	Primary:  To demonstrate, through absence of revision at 5 years postoperative, that acetabular replacement with the Tritanium® Acetabular Shell provides clinical results comparable to similar acetabular components.  Secondary:  • To study rates of screw fixation usage in Tritanium®					
	Acetabular Shell (cluster hole) procedures and compare with those reported in the Trident® X3® Polyethylene Insert Study.					
Objectives	To compare pain, function and health related quality of life (QOL) between the Tritanium® Acetabular Shell combined group and the above-referenced historical control group. The following outcomes measures will be used for this comparison:					
	
 
Harris Hip Score (HHS)
 
Short Form-12 (SF-12)
 
Lower Extremity Activity Scale (LEAS)
 
EQ-5D
 
					
	1-year, 3-year, and 5-year HHS, SF-12 and LEAS data will be compared to the historical control with respect to improvement from preoperative scores. The EQ-5D data will be summarized and presented.					

	An additional Follow-Up Questionnaire will be
	administered annually in postoperative years 6-10 to
	assess patient satisfaction and pain, and to capture
	adverse events. This questionnaire will provide the
	survivorship information necessary to evaluate the
	primary objective of the study.
Objectives	To review radiographic stability and complications
	between those hips implanted with the Tritanium®
	Acetabular Shell and those in the historical control
	group.
	Published complication rates with similar devices, as
	well as complications related to cementless acetabular
	replacement, will be reviewed.
	Cases will be enrolled until 240 cases have received the Tritanium® Acetabular Shell
Number of Subjects	
 
Treatment 1: 120 cases with X3® polyethylene insert
 
Treatment 2: 120 cases with MDM™ liner and ADM/MDM™ X3® insert
 

	Inclusions:
	A. Patient has signed an IRB approved, study specific
	Informed Patient Consent Form.
	B. Patient is a male or non-pregnant female age 18 years
	or older at time of study device implantation.
Diagnosis and Main	C. Patient has primary diagnosis of Non-Inflammatory
Inclusion/Exclusion Criteria	Degenerative Joint Disease (NIDJD).
	D. Patient is a candidate for a primary cementless total hip
	replacement.
	E. Patient is willing and able to comply with postoperative
	scheduled clinical and radiographic evaluations and
	rehabilitation.

	Exclusions:

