#### Statistical Methodology

- A two-sample t-test or Wilcoxon test will be used to compare the HHS, SF-12 and LEAS score at 1-year, 3-year, and 5-year follow-up between the Tritanium® Acetabular Shell and Trident® X3® Polyethylene Insert studies. If there are any statistically significant differences in baseline variables (e.g. age, gender, diagnosis) between the groups, they will be addressed as covariates and ANOVA or ANCOVA will be used.
- EQ-5D health states will be converted to numerical results using the appropriate value set and presented in table format.
- Adverse event (AE) rates will be listed and tabulated, with 95% confidence intervals presented.
- Radiographic data will be summarized in table format.

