#### 2.1.2 Secondary

Usage of bone screw fixation will be recorded and compared between the Tritanium® Acetabular Shell group and the Trident® HA Hemispherical Shell group (Trident® X3® Polyethylene Insert Study).

Additionally, pain, function and health-related QOL data for the Tritanium® Acetabular Shell group will be collected at postoperative time points and compared with the subjects' preoperative status, as well as with the historical control group and with published literature for similar highly porous acetabular shells. It is expected that the HHS, SF-12 and LEAS outcomes in the study group will be comparable to the historical control. It is expected that the EQ-5D outcomes in the study group will be comparable to published results for similar devices.

Lastly, radiographic stability and complications between those implanted with the Tritanium® Acetabular Shell and the historical control group will be reviewed.

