### 7 Evaluations

#### 7.1 Preoperative Visit

During the preoperative visit, patients that are possible candidates for this study will be screened to determine if they meet the inclusion/exclusion criteria. If the patient is a candidate, the investigator will propose participation in the study to the patient, according to GCP guidelines. Patients must sign an IRB approved study consent form prior to participating in any study related activities. Consent must be obtained within four months of surgery.

Once the subject has been consented, preoperative data will be collected including: demographics, medical history, HHS, AP hip, AP pelvis and lateral radiographs, SF-12, LEAS and EQ-5D.

All preoperative data must be collected within 4 months of the scheduled date of surgery, with the exception of radiographs, acceptable within 1 year of the scheduled date of surgery. All information collected preoperatively will be used to quantify the sample population and compare postoperative progress.

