### 9.1.2 Secondary Efficacy Parameters

The secondary efficacy parameters include:

- The usage of screw fixation
- HHS at the 1-, 3- and 5-year follow-up visits
- SF-12 scores at the 1-, 3- and 5-year follow-up visits
- LEAS at the 1-, 3- and 5-year follow-up visits
- EQ-5D at the 1-, 2-, 3-, 4- and 5-year follow-up visits
- Follow-Up Questionnaire annually in postoperative years 6-10

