### 9.1.5 Secondary Efficacy Analysis

A two-sided 0.05 alpha level will be used.

For comparison of usage of bone screw fixation between the Tritanium® Primary Acetabular Shell Study and the Trident® X3® Polyethylene Insert Study, a Chi-square test or Fisher's exact test will be used. If there are any statistically significant differences in baseline variables (e.g. age, gender, diagnosis) between the groups, they will be addressed as covariates and ANOVA or ANCOVA will be used.

For comparison of HHS, and SF-12 and LEAS at 1, 3 and 5 years postoperative between the Tritanium® Acetabular Shell and Trident® X3® Polyethylene Insert studies, a t-test or Wilcoxon test will be used. If there are any statistically significant differences in baseline variables (e.g. age, gender, diagnosis) between the groups, they will be addressed as covariates and ANOVA or ANCOVA will be used.

EQ-5D values and changes from baseline will be presented for each interval. Data from the Follow-Up Questionnaire will be used as an input to the Kaplan-Meier survival curve for postoperative years 6-10; any adverse events collected via the Follow-Up

Questionnaire will be reported on a separate Adverse Event eCRF and included in the safety analysis.

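### The synopsis is inconsistent on whether HHS, SF-12 and LEAS are compared with the historical control as improvement or as score at the visit, and adjustment depends on a significant baseline test

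*Combined protocol and SAP*

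**What the plan says.** All references are to the combined protocol and SAP.

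**Outcome**
- Study Synopsis, Objectives: the 1-, 3- and 5-year data are "compared to the historical control with respect to improvement from preoperative scores".
- Study Synopsis, Statistical Methodology: the two-sample test "will be used to compare the HHS, SF-12 and LEAS score at 1-year, 3-year, and 5-year follow-up".
- Section 9.1.2 lists, for example, "HHS at the 1-, 3- and 5-year follow-up visits", and gives SF-12, LEAS and EQ-5D in the same form.
- Section 9.1.5 names HHS, SF-12 and LEAS at 1, 3 and 5 years without saying score or change. For EQ-5D it adds "EQ-5D values and changes from baseline will be presented for each interval".
- Section 2.1.2 sets the data against the subjects' "preoperative status, as well as with the historical control group and with published literature". Section 7.1 says "All information collected preoperatively will be used to quantify the sample population and compare postoperative progress".

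**Adjustment**
- Section 9.1.5: "a t-test or Wilcoxon test will be used. If there are any statistically significant differences in baseline variables", followed by covariate adjustment through ANOVA or ANCOVA.
- The synopsis methodology has the same condition: "statistically significant differences in baseline variables (e.g. age, gender, diagnosis) between the groups, they will be addressed as covariates". The list of variables is open, and the preoperative score is not named in it.

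The comparator is a separate study (the Trident X3 insert study), and section 5.2 states that enrolment is non-randomised.

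**The concern.** Two choices are left open for one set of comparisons: what is compared (score at the visit or change from before surgery), and whether it is adjusted.

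A significance test at baseline is a poor guide to the second choice. Its p-value depends on sample size as well as on the gap between the studies, and it does not show whether the variable confounds the comparison. With a separate, non-randomised control, some baseline difference should be expected.

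The two choices interact. If the preoperative score is not in the model, the score and change readings can give different answers. If it is in a linear model, they give the same answer. So the inconsistency in the outcome matters whenever the trigger does not bring the preoperative score in. What is at stake is whether the result reported against the historical control is one estimate fixed in advance or one of several that the text allows.

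**Working it through.** The plan gives no sample size, SD or margin for these outcomes, so it has no figure of its own to reproduce.

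**1. Text.** The objectives say improvement and the methodology says score at follow-up; these differ. Section 9.1.2 lists EQ-5D in the same at-the-visit form as HHS, yet 9.1.5 presents changes in EQ-5D. That form therefore gives timepoints and does not exclude change. Sections 2.1.2 and 7.1 fit the improvement reading but do not define the between-study outcome.

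**2. How the readings relate.** Let D be the observed difference between studies in mean preoperative score.
- Unadjusted means: (difference in score) − (difference in change) = D.
- Linear model with the preoperative score B: change = a + τ·study + β·B is the same model as score = a + τ·study + (β + 1)·B. The study effect τ is identical.

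**3. Inputs**
- Study cases: 240 × 0.8 = 192 (enrolment and 20% loss, section 9.4.2).
- HHS SDs: 13.8 before surgery and 6.2 at latest follow-up. Section 1.1 reports them for a different cup at 8 to 10 years.
- Assumed, not in the documents: 192 controls (range 100-300); pre/post correlation r = 0.5 (checked at 0.3); baseline tests at two-sided 0.05; the preoperative score is among the variables tested and enters the model if significant; no device effect.

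**4. Largest gap left unadjusted**
- SE = 13.8 × √(2/192) = 1.408.
- c = 1.96 × 1.408 = 2.76 HHS points (3.34 with 100 controls, 2.50 with 300).

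**5. Average difference between the readings under the rule.** With D ~ N(g, SE), this is E[D·1(|D| < c)] = g·P(no trigger) + SE·[φ((−c−g)/SE) − φ((c−g)/SE)]. For g = 0.15 SD = 2.07 points: 2.07 × 0.688 + 1.408 × (0.001 − 0.354) = 0.93.

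| True gap (SD) | Trigger fires | Average difference (points) |
|---|---|---|
| 0 | 5% | 0.00 |
| 0.05 | 8% | 0.47 |
| 0.15 | 31% | 0.93 |
| 0.20 | 50% | 0.82 |
| 0.30 | 84% | 0.33 |
| 0.40 | 98% | 0.06 |

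For 192 per group, 0.93 is about the maximum. At 0.15 SD, control sizes of 100 to 300 give 1.08 to 0.83 points and a trigger rate of 23% to 37%.

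**6. Precision.** The 95% CI half-width is 1.96 × SD × √(2/192).
- Change: SD = √(13.8² + 6.2² − 2r × 13.8 × 6.2) = 13.32 (r = 0.3) or 11.97 (r = 0.5), giving 2.67 or 2.39.
- Score: SD 6.2, giving 1.24.
- ANCOVA: SD = 6.2 × √(1 − r²) = 5.91 or 5.37, giving 1.18 or 1.07.

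A check with HHS capped at 100 (tuned to mean 97.0, SD 6.2; r = 0.5 before capping) gave 2.54 for change, 1.21 for score and 1.13 for ANCOVA.

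**7. Bias.** Simulation with 8,000 replicates, gap 2.07 points, r = 0.5. In A the gap acts through a linear baseline effect; in B it simply persists to follow-up.

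| Estimate (HHS points) | A | B |
|---|---|---|
| Plan's rule, score | +0.2 | +1.8 |
| Plan's rule, change | −0.7 | +0.9 |
| ANCOVA always | 0.0 | +1.6 |
| Unadjusted change | −1.6 | 0.0 |

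**The case against.** The strongest reply is that this is one loose line in the synopsis. The objectives state improvement, 2.1.2 and 7.1 fit it, and 9.1.2 and 9.1.5 need mean no more than timepoints. That stands in large part. A reader might infer that three places contradict one, but the documents support a clear conflict only within the synopsis, with the body of the plan silent.

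The open variable list also lets the preoperative score be tested and adjusted for. That is correct: the plan permits it but does not require it.

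On size, the 0.93-point figure is close to the worst case for 192 per group and falls to nearly zero for both very small and large gaps. It is under 2% of the improvement in section 1.1 (97.0 − 44.0 = 53.0 points; 0.93/53.0 = 1.8%). That stands too.

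On bias, a reader might infer that dropping the trigger always brings the estimate closer to the truth. The simulation does not support this. On the change reading, ANCOVA gains about 0.7 points in A and loses about 0.7 in B; on the score reading it gains about 0.2 in each. The precision gain over the unadjusted score is also small, at 0.06 to 0.17 points.

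The reply does not remove the inconsistency in the synopsis or the dependence of the model on a baseline p-value.

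**Conclusion.** The point holds at minor to moderate weight. The synopsis gives two different outcomes for the same comparison, the body of the plan does not settle which applies, and adjustment of a non-randomised comparison depends on a significance test that does not measure confounding.

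The demonstrated benefit of a fixed model is a single result chosen in advance and, on the change reading, a confidence interval about half as wide or less. No uniform reduction in bias is shown.

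It would be tempting to say that the two readings always differ by exactly the observed preoperative gap. That is true only of unadjusted mean differences. It does not apply to a Wilcoxon test, or to a model in which only another variable, such as age, triggered adjustment.

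The figures rest on the assumed control size, correlation and gap, and on HHS SDs from another device at later follow-up. They are for HHS only. These outcomes are secondary and have no margin; the primary revision analysis and its sample size are unaffected.

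**What to change.** 1. In the synopsis methodology and sections 9.1.2 and 9.1.5, name the outcome for HHS, SF-12 and LEAS as change from the preoperative score, in line with the synopsis objectives.
2. For these scores, replace the significance trigger in the synopsis methodology and 9.1.5 with an ANCOVA fixed in advance. It should contain study and preoperative score, plus age, sex and diagnosis where the control data hold them. Report the adjusted difference with its 95% CI at 1, 3 and 5 years.
3. Show the unadjusted difference in mean change with its 95% CI beside it, and keep the Wilcoxon test as a check for the HHS ceiling.
4. State that neither estimate is free of bias: ANCOVA is biased if the baseline gap simply persists, and unadjusted change is biased if the gap acts through a linear baseline effect. State also that a non-significant difference does not show comparability.

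Cost: a few wording changes and a little more analysis. Section 7.1 already collects the preoperative scores and demographics in this study. The synopsis describes the control study's data as a close match, but which covariates it recorded must be checked.

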### 9.2 Safety Parameters

### 9.2.1 Safety Parameters

Safety parameters will include:

- All AEs reported
- Radiographic stability at each postoperative visit
- Revision or removal rates

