#### Radiographic Outcomes:

To assess radiographic stability as compared with the historical control, radiographs will be taken and collected in the AP pelvis, AP hip and lateral views for the preoperative, 6-week, 1, 3 and 5-year intervals. Additional radiographs will be obtained at the 7-year and 10-year time points at investigational sites that choose to bring their subjects back in for these optional visits.

The AP pelvis and AP hip views allow for observation of any conditions involving the sacral wings, iliac bones, ischium, pubis as well as the femoral head and neck. The lateral view allows for evaluation of the entire hip joint as well as the femoral head, neck and proximal shaft. Suggested radiographic technique for the views required is included in Appendix A.

Radiographs will be evaluated by an independent reviewer throughout the course of the study. Radiographic analysis of the acetabular component will employ three zones (Zone 1 – Zone 3) in the AP views. Numerous parameters will be reviewed by zone, including radiolucency and migration. Radiolucency in at least 50% of a zone and measuring at least 1 mm in width is defined as radiolucency present. Cases that present with migration of greater than 5 mm in any direction or at least 2 mm radiolucency in all zones will be considered radiographic failures.

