### 9.2.2 Safety Analysis

All AEs will be listed, tabulated and summarized by event, number and percent of cases/subjects. AE rates and 95% confidence intervals will be presented.

For categorical variables, such as radiographic stability, the number and percent in each category will be presented.

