### 9.3 Missing Data

No missing data will be imputed for the primary analysis and secondary analyses.

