### Termination Reason Date of Termination

Death Date of death

Investigative center termination Date of study close-out visit

Lost to follow-up Date Stryker termination approval given

Voluntary withdrawal Date subject notified center of withdrawal

Revision/removal of study device Date of revision/removal procedure

Study device not implanted

Surgery not performed

Date of surgery

Date Stryker termination approval given

At the time of study surgery it is required that the following components are implanted:

- Tritanium® Acetabular Shell
- Stryker X3® polyethylene inserts (120 cases)
- Stryker MDMTM liners with ADM/MDMTM X3® polyethylene inserts (120 cases)
- Stryker LFIT™ CoCr heads, BIOLOX *delta* or alumina ceramic heads
- Stryker Universal Adapter Sleeves (for use with BIOLOX delta universal ceramic heads)
- Compatible Stryker femoral stems
- Stryker Orthopaedics Torx Bone Screws

Revision or removal of the Tritanium® Acetabular Shell constitutes a failure and study termination for the subject.

If MDMTM liner, acetabular insert (either X3® or ADM/MDMTM X3®) or femoral head exchange is required during the study, the event is considered a reoperation and does not constitute a failure or study termination.

If femoral stem revision is required during the study, the event is considered a reoperation and does not constitute a failure or study termination.

If the subject fails to return for his/her follow-up appointments, every effort should be made to contact the subject to assess his/her health status. If after attempting to contact the subject through three documented phone calls and a certified letter, the subject still does not respond, he/she will be considered lost to follow-up. A Study Termination eCRF will be completed only after notifying Stryker of the subject's status and being given approval to terminate.

In the event a subject does not have surgery, Stryker should be contacted to discuss if/when the surgery will be rescheduled. If the surgery is rescheduled more than 4 months from the date of preoperative data collection, the subject will need to be re-consented, all preoperative data will need to be re-collected and all original preoperative data will need to be removed from the database. If the surgery is not to be rescheduled or if the subject is no longer considered an

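### Radiographic stability is summarised visit by visit, so shells already revised for loosening or migration drop out of later percentages and the comparison with the historical control covers only shells still in place

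*Combined protocol and SAP*

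**What the plan says.** Section 9.2.1 names three safety parameters: adverse events, "Radiographic stability at each postoperative visit", and revision or removal rates. On the second, Section 9.2.2 says: "For categorical variables, such as radiographic stability, the number and percent in each category will be presented". No denominator is given.

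Under Radiographic Outcomes in Section 2.1.2, cases with "migration of greater than 5 mm in any direction or at least 2 mm radiolucency in all zones will be considered radiographic failures". The definition rests on the film alone; revision for loosening is not part of it. Films are taken in AP pelvis, AP hip and "lateral views for the preoperative, 6-week, 1, 3 and 5-year intervals", with 7 and 10 years optional. The same section sets radiographic stability against the historical control.

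Section 10.3 states that revision or removal of the Tritanium "Acetabular Shell constitutes a failure and study termination for the subject", and its termination table gives the date to use: "Revision/removal of study device Date of revision/removal procedure". Section 9.3 says: "No missing data will be imputed for the primary analysis and secondary analyses". No section carries an earlier radiographic failure forward, and none plans a cumulative radiographic outcome.

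**The concern.** A percentage taken at each visit describes the hips that reach that visit. Shell revision removes a hip from every later visit, and revision for loosening or migration removes exactly the hips that the radiographic endpoint is meant to detect. The required films are two years apart after year 1, so a hip can also loosen and be revised between films without ever being read as a failure.

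The radiographic result is compared with the historical control, and Section 1.2 says the study collects data to support claims of improved initial and biological fixation. If loose shells are revised sooner in one study than in the other, the per-visit percentages can differ even when the same proportion of shells lost fixation.

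**Working it through.** The plan gives no expected figure for radiographic stability, so there is none to reproduce. The inputs taken from Section 9.4.2 are 240 cases, 20% loss by 5 years, 99% assumed success, a literature range starting at 97.9%, and a 5-point margin (94%). The number of unstable hips and the share of revisions due to loosening are my assumptions, shown as ranges.

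**1. Following a hip through the rules.**
- It fails on the 1-year film and is not revised: it stays available for every later visit table.
- It fails on the 1-year film and is revised at 2 years: it is a failure in the 1-year table and absent at 3 and 5 years.
- It has a clear 1-year film, then loosens and is revised at 2 years: it is never a radiographic failure in any table.

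**2. Effect on one denominator.** Let N be hips implanted, U hips ever unstable by 5 years, and R those of U already revised, with no other losses. If the percentage is of hips filmed, the visit figure is (N − U)/(N − R). A cumulative figure that keeps revised-for-loosening hips as failures is (N − U)/N. Assume N = 240 and U = 12 (5%).

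| R | Visit table, stable | Cumulative, stable |
|---|---|---|
| 0 | 228/240 = 95.0% | 228/240 = 95.0% |
| 6 | 228/234 = 97.4% | 228/240 = 95.0% |
| 12 | 228/228 = 100% | 228/240 = 95.0% |

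**3. Size at the plan's own revision rates.** After 20% loss, N = 240 × 0.8 = 192. The rates are 1% (base assumption), 2.1% (100 − 97.9) and 6% (100 − 94). These give 1.92, 4.03 and 11.52 hips, taken as 2, 4 and 12. Assume no unrevised hip is unstable, so the visit table reads 100%. With L revisions for loosening, the cumulative figure is (192 − L)/192.

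| Revised | All for loosening | Half for loosening | None for loosening |
|---|---|---|---|
| 2 (1%) | 190/192 = 99.0%, gap 1.0 | 191/192 = 99.5%, gap 0.5 | gap 0 |
| 4 (2.1%) | 188/192 = 97.9%, gap 2.1 | 190/192 = 99.0%, gap 1.0 | gap 0 |
| 12 (6%) | 180/192 = 93.8%, gap 6.2 | 186/192 = 96.9%, gap 3.1 | gap 0 |

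Gaps are in percentage points. Revisions for other reasons hardly matter: with 4 unrevised unstable hips and 2 stable shells revised, the visit table gives 186/190 = 97.89% and the cumulative figure 188/192 = 97.92%.

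**4. If the denominator were all 240 hips instead.** Percent stable would stay at 228/240 = 95.0%, but percent unstable would fall from 12/240 = 5.0% to 6/240 = 2.5% and then 0% as 0, 6 and 12 hips are revised. The failures still leave the table, by another route.

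**The case against.** The strongest reply is that these hips are reported elsewhere in the same safety section. Revision or removal rates are listed directly beneath radiographic stability. Operative-site adverse events are reportable whatever their seriousness (Section 8.1), including between visits (Section 8.4). The adverse event form has boxes for acetabular loosening and for migration above 3 mm, a lower threshold than the 5 mm film criterion. Section 9.2.2 tabulates these events with 95% confidence intervals, and Section 9.1.4 adds a Kaplan-Meier curve of revision. A hip that loosens and is revised between films should therefore appear as an adverse event, a revision and a primary failure. This stands, and it confines the point to the radiographic table. It does not repair that table. The revision results cover every cause, infection and dislocation included, and nothing combines loosening events with film failures into one result to compare with the control.

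Other parts of the reply also stand:
- Earlier film failures stay in their own visit's table.
- No test is planned on the radiographic data.
- The effect is probably small. Section 1.1 cites 0.7% revision for aseptic loosening at 8.5 and 9.5 years for two other surfaces. In its two primary hip series (147 and 156 hips), the six acetabular revisions were four for infection and two for dislocation. The first series also had one report of acetabular loosening.

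The unstated denominator works both ways. The plan does not say that the percentage is of hips filmed, so the rise in percent stable in step 2 is conditional on that reading. The silence is itself a reason to specify it.

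**Conclusion.** The point holds as a survivorship bias limited to the radiographic summary and its comparison with the historical control. Its size is bounded by the proportion of hips revised for loosening or migration: about 1 percentage point at most at the planned 1% revision rate, near zero if no revision is for loosening, and about 6 points if revision reached the 6% margin and all of it was for loosening. The example running from 95.0% to 100% rests on an assumed 12 unstable hips among 240, no other losses, and a denominator of hips filmed.

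Three stronger readings are tempting, and the documents do not support them:
- A reader might infer that loosened hips vanish from the report. They do not, because the adverse event, revision and primary results include them.
- A reader might infer that the comparison is shown to favour the study shell. The documents do not say how soon loose shells were revised in the historical study or how its percentages were formed, so neither the direction nor the net size is known.
- A reader might set 6 failures among about 190 filmed hips (3.2%) beside 6 of 240 (2.5%) and attribute the whole swing from 3.2% to 0% to the timing of revision. The excess of 3.2% over 2.5% comes from assuming that all six failures stay in follow-up while about 50 other hips are lost. On a single denominator there is no gap when nobody is revised.

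This is a worthwhile, inexpensive improvement and does not threaten the primary analysis.

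**What to change.** In Sections 9.2.1 and 9.2.2, add a cumulative incidence by 1, 3 and 5 years, with 95% confidence interval, of the first of two events: radiographic failure by the Section 2.1.2 criteria, or shell revision or removal for loosening or migration. Include all implanted hips. Treat death and shell revision for other reasons as competing events. Censor other hips at the last date on which both film and revision status are known.

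Keep the per-visit table, head it *unrevised hips with an evaluable film*, and state its denominator.

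Apply the same definition to the historical control where its case-level data allow. The synopsis says only that the control's intervals and data closely match, so this cannot be taken for granted. If it is not possible, show the control's revisions for loosening beside its per-visit percentages.

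The cost is SAP wording and one extra table. For the study hips, the films, revision dates and event types are already collected, so no visit or procedure is added. The downside is a slightly less favourable stability figure; the control may need extra data work.
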